18.0 APPENDIX

18.1 Dietary Recall Script

CLOSED EFFECTIVE 5/15/2020

18.1 Dietary Recall

a. Script

The Arizona Diet, Behavior, and Quality of Life Assessment Lab NDSR- Phone Script (For use with the University of Minnesota's Nutritional Data System for Research). Interview may be conducted with the patient or designated caregiver/companion. The patient is the preferred respondent; if the patient's health makes it difficult for him/her to report, the surrogate caregiver will report. Documentation of who responded will be made on the call record by the interviewer. Contact will be made by telephone on randomly assigned days per protocol (days to call are generated from a randomization program used by the shared service at the University of Arizona Cancer Center). If the participant and his/her caregiver decline to complete the interview on a given day (as patients may feel ill or fatigued), the call will be rescheduled within 4 days.

INTRODUCTION:

Hello, my name is _____ and I am calling from the University of Arizona Diet lab for the malignant bowel obstruction study you are participating in through _____ (fill in Site name from Contact sheet).

_____ (Fill in Head Nurse/CRA's name, or if unavailable, say: The nurse who consented you to this study from the hospital) gave us your contact information so that we can begin the calls to collect information on what you are eating. You may remember that these calls were described in the study consent form. Today's call should not take more than 20 minutes and likely much less of your time. I need to ask you about what you ate yesterday.

(IF NEEDED: The length of time it takes varies greatly from person to person depending on whether you are eating or not.)

May I begin the diet recall with you now?

(IF NOW IS NOT CONVENIENT: When would be a good time to call you back to do the recall? It is important for the study that the recall is conducted within the next 24 hours.)

I am going to begin by asking you to answer a few brief questions about how you consume your food and with whom you share your meals:

3. In describing what you ate/consumed yesterday which of the following seems most accurate? I will read you 6 different options:

- a. I am not eating or drinking anything (except maybe water or ice)
- b. I am on tube feeding only
- c. I am on tube feeding but eat small amounts of food
- d. I am consuming only liquids (beverages including juice, milk, shakes, etc. as well as soups, Jell-O®, pudding, , ice cream, etc.) this may include liquid high calorie/protein beverages, but other liquids also)
- e. I am consuming only liquid nutritional supplements such as Boost®, Ensure® and no other solid food or liquids
- f. I am eating liquids and solids (such as fruit/vegetables, cereal, bread, meat, eggs, cheese, cottage cheese, pastries/sweets, etc.), but more liquids

g. I am eating both liquids and solids, but more solids

4. Did you share any meals yesterday with a family member, friend or care giver? Yes No

If Yes, which of your meals or snacks yesterday were eaten with others?

- a. All
- b. Breakfast
- c. Lunch
- d. Dinner/supper
- e. Snacks

Based on response the interview will continue; response (a) from Questions 1 (tube feeding only) will trigger a closure of the interview at this point. I am now finished with the interview questions. Do you have any questions at this point? We plan to call you again in about 4 weeks. I hope you have a good day.

Since you are taking in foods by mouth, I am next going to have you tell me when and what you ate yesterday. After midnight the day before yesterday (state day of week), what was the first time after waking that you recall having something to eat or drink?

What did you have to eat or drink at that time?

Did you have anything else to eat or drink at that time?

When was the next time you had something to eat or drink?

What did you have at that time?

Did you have anything else at that time?

(THE LAST THREE QUESTIONS ARE REPEATED UNTIL THE PARTICIPANT SAYS THAT HAD NOTHING ELSE TO EAT OR DRINK YESTERDAY. THEN THE QUICK LIST IS REVIEWED WITH THE PARTICIPANT).

At (at time) you had (read recorded food items). Can you think of anything else you had at that time?

IF NEEDED PROBE: Did you have a beverage with that meal?

IF NEEDED PROBE: Did you have any snacks between meals or did you sample foods as you prepared the meal?

How much did you eat/drink?

(THE SECTION ABOVE IS REPEATED FOR EACH INDIVIDUAL FOOD ITEM)
We are almost done, but I'd like to review the day with you once more just to make sure I have entered everything correctly.

At (time) you had (amount) of (food). Is this correct?

Did you have anything else at that time?

(REPEAT FOR ALL FOODS)

ADDITIONAL QUESTIONS FOR MBO

5. Was this a typical day in relation to your eating pattern over the past week (in terms of your diet habits)?
 - a. Yes,
 - b. No, (SPECIFY REASON)

6. Please tell me if the amount of food you consumed yesterday was
 - a. close to the amount you usually have
 - b. a lot more than usual (SPECIFY REASON) or
 - c. a lot less than usual (SPECIFY REASON)?

7. Did you experience any problems that may have altered your eating or food choices yesterday such as:

Symptom	IF YES, ATE MORE OR LESS
a. Sore stomach,	More / Less
b. Bloating/gas,	More / Less
c. No appetite,	More / Less
d. Significant constipation,	More / Less
e. Diarrhea, or	More / Less
f. Too tired to eat?	More / Less
g. OTHER PROBLEM (SPECIFY)	More / Less

Please tell me of any foods you are avoiding and why:
(no raw foods, no dairy, no gluten, etc. [SPECIFY]; can't digest, constipated, too much gas, etc.) (Rationale)

I have finished the interview questions. Do you have any questions at this time?
We plan to call you again in about 4 weeks. I hope you have a good day.

b. Quality Control

Quality control procedures have been established and are fully implemented for the 24-hour dietary recall data collection, coding, and entry process. Regular meetings are held to discuss and solve problems to ensure that the quality of dietary data provided by study participants is excellent. Complete sets of checked and corrected recalls are sent to The Arizona Diet, Behavior, and Quality of Life Assessment Lab where they are coded and entered. The 24-hour dietary recall quality control/quality assurance (QC/QA) procedures include a 25% duplicate entry of recalls by a different coder, followed by a comparison of entered recalls and reconciliation. Discrepancies attributable to coder error are addressed by closer surveillance and retaining when necessary. Whenever differing interpretations of a subject's data set are identified, the entire 4-day recall set is reviewed to provide consistency of coding. In general, the differences found in the quality control process are minor.

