7.4 Dietary Recall

Dietary recalls are a self-reported diet measurement method that relies on the patient (or caregiver) to report all foods consumed in the prior 24-hour period. Standard USDA multi-pass methodology will be used to collect this self-reported information by telephone. The Dietary Recall will be collected by trained staff at the Arizona Diet, Behavior, and Quality of Life Assessment Lab. The patient or their representative will be contacted every 4 weeks by phone for up to one year after registration to conduct 24-hour dietary recalls. The patient will be queried on food and beverage consumed during the past 24-hours. The recalls will be qualified in terms of frequency of meals, primarily liquid, solids or mixed, use of feeding tubes/formulas as well as coding for commonly reported food avoidances. Patients will also be queried as to whether the 24-hour recall is typical of their intake in recent days, and if not how the intake differed (more liquid foods, less vegetables, avoidance of foods they are not tolerating) as well as when they recall making this change (by date of change). Each call will last on average about 15-20 minutes.

The patient and their representative's contact information will be collected at the baseline visit on the **S1316** Dietary Recall Contact Form and will be sent to the Arizona Diet, Behavior, and Quality of Life Assessment Lab via e-mail (scanned and sent as an attachment). Always follow your institutional HIPAA policies when emailing protected health information (PHI).

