11.4 Secondary analyses

A strategy similar to that used for the primary endpoint will be employed for secondary endpoints. For other HR-QOL type endpoints (e.g., ability to eat, days of nasogastric tube, intravenous hydration, solid food, etc.) we will examine the distribution properties of these variables and determine whether a normal approximation is adequate, or whether a transformation would be required or another generalized linear model would be preferable. For failure time endpoints, such as overall survival, the analyses will be based on a Cox regression model where we will have the option of stratifying on study component and selected other key covariates rather than modeling them in the regression. QALY-adjusted analyses will incorporate the EQ-5D-5L, as described in Cheville et.al. (44)

Specific to dietary outcomes we will describe total self-reported energy intake, macronutrient intake in patients with MBO and relation to time since MBO and if this differs for those undergoing surgery versus no surgery. Similarly we will evaluate the same associations with the dietary exposure of interest being frequency of meals and alternately composition of meals (liquids, solids, mixed, feeding formulas [oral or enteral]).

Adherence adjusted analyses: Although the primary analysis will be based on the intent to treat (ITT) principle, if a substantial fraction ($> 30\%$) do not receive the initially assigned/chosen treatment, we will conduct a sensitivity analysis that takes into account the patient's received treatment through inverse probability weighting.

In exploratory analyses we will examine the extent to which we can identify subgroups of patients for whom differences in treatment effects may differ from the overall result, i.e.,

are there subgroups of individuals for whom surgery is particularly beneficial or particularly contra-indicated? To address this question, the final model for the primary analyses in the pooled data will be expanded using interaction terms between selected baseline factors and treatment assignment.

Sample sizes permitting, those of particular interest will be analyzed based on the following hypotheses:

1. Patients with ascites who undergo a surgical procedure will have poorer outcomes than those who are treated by non-surgical management.
2. Patients who have albumin < 3.0 who undergo a surgical procedure will have poorer outcomes than those who are treated by non-surgical management.

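### The dietary recall skip rule contradicts the answer list it refers to, and the plan does not say how a closed interview enters the energy-intake description

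*Combined protocol and SAP*

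**What the plan says.** Section 18.1 gives the telephone script. The screening item, introduced by "3. In describing what you ate/consumed yesterday which of the following seems most accurate", announces 6 options and lists seven, (a) to (g). The first is for patients with no intake: "a. I am not eating or drinking anything (except maybe water or ice". The second, for those fed wholly by tube, reads "b. I am on tube feeding only". The third, (c), covers tube-fed patients who also take a little by mouth.

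A question on shared meals (4) follows. Then comes the skip rule: "response (a) from Questions 1 (tube feeding only) will trigger a closure of the interview at this point". Patients who are not closed out hear a lead-in that takes oral intake for granted, and go through the itemised recall. After that come questions 5 (typical day), 6 (amount compared with usual) and 7 (problems that altered eating), and an item on foods avoided.

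Section 7.4 says the recalls will capture use of feeding tubes or formulas and commonly avoided foods. Patients will also be asked whether the day was typical, how intake differed if it was not, "as well as when they recall making this change (by date of change". No exception is made for patients who take nothing by mouth.

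Section 11.4 plans to describe energy and macronutrient intake and whether they differ between surgery and no surgery. It plans the same for meal frequency and for "composition of meals (liquids, solids, mixed, feeding formulas [oral or enteral".

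**The concern.** An interviewer cannot obey both halves of the rule. One half names answer (a); the other describes answer (b). Different interviewers could therefore treat the same patient differently, and one group with no oral intake is taken through questions written for people who eat.

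The closed group also loses data that the plan says it will collect. In a trial of bowel obstruction these are not marginal patients. Section 1.2 lists ability to eat among the outcomes to be compared, and Section 2.0 stresses how much it matters to know what patients can eat and drink. If closed interviews end up as missing values, the energy description covers only patients who eat, and eating may itself depend on treatment.

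**Working it through.** The plan gives no figure to reproduce here. The check traces each answer through the script, lists what a closed call contains, and then asks when this could affect the energy description.

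**Step 1: which answers close the call.** The rule can be read by its letter, by its label, or by the lead-in that follows it, which fits neither (a) nor (b).

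| Answer | By letter | By label | By lead-in |
|---|---|---|---|
| (a) takes nothing | closes | continues | closes |
| (b) tube feeding only | continues | closes | closes |
| (c) to (g) | continue | continue | continue |

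The rule as worded closes one of (a) and (b). Only the lead-in suggests closing both. Tube-fed patients who also eat, answer (c), continue on every reading.

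**Step 2: what a closed call contains.**

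- Obtained: mode of intake (question 3) and shared meals (question 4).
- Not obtained: the itemised recall, questions 5, 6 and 7, and foods avoided.
- For (a), question 3 already establishes essentially nil oral intake, so zero oral energy can be coded afterwards.
- For (b), question 3 places the patient in the enteral-formula category, but there is no product, volume, energy or macronutrient content. The script offers no way to recover these.

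**Step 3: other mismatches in the script.** Seven options are listed against 6 announced. No item asks for the date of a dietary change, although Section 7.4 promises it; questions 5 and 6 ask only for a reason, and the avoidance item asks what and why.

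**Step 4: when the energy description would be affected.** No section says how a closed call is coded. The missing-data paragraph in Section 11.3 deals only with prevention. Let M be mean intake among patients who eat, assumed equal in both groups, and let p_s and p_n be the shares closed out under surgery and no surgery.

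*If (a) is the closed group:*

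- Coded zero: difference (surgery minus no surgery) = (1 − p_s)M − (1 − p_n)M = (p_n − p_s)M.
- Coded missing: difference = M − M = 0.

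With assumed values M = 1,000 kcal and p_s = 10% (neither is in the documents):

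| p_n | Difference, coded zero | Difference, coded missing |
|---|---|---|
| 10% | 0 kcal | 0 kcal |
| 20% | 100 kcal | 0 kcal |
| 30% | 200 kcal | 0 kcal |
| 40% | 300 kcal | 0 kcal |

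Interchanging p_s and p_n reverses the sign.

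*If (b) is the closed group:* let F be mean formula energy. The all-patient difference is (p_n − p_s)(M − F), against 0 if coded missing. Its sign depends on whether F is above or below M, and a closed call does not record F.

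The treatment comparison is distorted only if closed calls are treated as missing, the closed share differs between groups, and the closed patients' intake differs from that of patients who eat.

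**The case against.** The strongest reply is that little is lost. Question 3 is itself an intake question and is asked before closure. It records that a patient takes nothing or is tube-fed, and so supports the broad composition categories in Section 11.4. The dietary analysis is secondary and descriptive. Ability to eat and solid food are listed there as endpoints in their own right, so the comparison of eating does not rest on recall energy alone. All of this stands, and it limits the point.

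It also rules out several stronger readings that a reader might infer:

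- That the interview ends before any intake question, or leaves no intake record. Questions 3 and 4 come first.
- That all patients who cannot eat or are tube-fed drop out. The rule as worded closes one of (a) and (b), and never (c).
- That the energy comparison is biased toward the group with more non-eaters. No section says closed calls are missing or excluded, and none gives the non-eating share by group.
- That the prompted problems in question 7 are deficient because they omit nausea and vomiting. The MDASI-GI measures both, weekly to Week 13 and then every 4 weeks, and question 7 allows other problems to be specified.

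The rule's reference to question 1, where the item is printed as 3, may come from list numbering in the PDF and carries no weight. A stale cross-reference is plausible: without the present (a), six options would remain and tube feeding only would be first. The documents do not confirm this.

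The reply does not remove the conflict between letter and label, the skipped items, or the lack of a coding rule.

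**Conclusion.** The point holds in limited form and is worth correcting. It is certain from the text that the rule's letter and label conflict, and that a closed call omits the itemised recall, questions 5 to 7 and foods avoided. If tube-only patients are closed, their formula energy and macronutrients are not collected in this script.

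Any effect on the surgery versus no-surgery energy description is conditional on the three requirements in the working. The documents settle none of them, so neither size nor direction can be stated; the 0 to 300 kcal range is only an illustration on assumed inputs. The primary endpoint, days alive and out of hospital through day 91, does not use these data.

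**What to change.** **Script (Section 18.1).** Name both (a) and (b) in the skip rule. For (a), record zero oral energy. For (b), record formula product and volume. For both, ask whichever of questions 5 to 7 and the foods-avoided item apply, and then close. Change the announced number of options to 7, and add the date-of-change question promised in Section 7.4.

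**Analysis (Section 11.4).** Add one sentence: among patients alive at the call, answer (a) enters the energy and macronutrient summaries as zero oral intake and answer (b) as formula intake.

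**Calls already made.** The protocol is stamped closed effective 5/15/2020, so this may be the part that matters most. Use question 3 to code (a) as zero, and report tube-only patients separately by treatment group, since their energy cannot be reconstructed from a closed call.

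The cost is a script edit, one analysis sentence, and a minute or two on each affected call.
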